7.9 Safety Analyses

Subject safety is assessed by AEs, labs, vital signs, 12-lead ECGs, and findings from the physical examinations. The occurrence of neurological side effects will be assessed by looking at any worsening in scores for each of the Simpson-Angus scale, Barnes Akathisia scale, and AIMS. Suicidal ideation and suicidal behavior will be measured by C-SSRS. All summaries related to safety analyses will use the safety population and will be presented by treatment groups.

7.9.1 Adverse Events

AEs will be summarized using subject incidence table by treatment period (titration, maintenance, combined titration and maintenance, and tapering). An overview of TEAE will be presented. This table will include numbers and percentages of subjects experiencing at least 1 TEAE, study drug-related TEAE, AE leading to study drug discontinuation, severe TEAE, serious TEAE, related TESAE, AESI, and TEAE with outcome of death (Table 14.3.1.1).

Additionally, the number and percent (%) are calculated based on the number of unique subjects within each category (e.g., preferred term) by treatment group. A subject reporting multiple events of the same category will be counted only once for that category. For summary purpose, AE relationship to the study drug will be grouped into "Unrelated" for "unrelated" or "unlikely related" and "Related" for "possibly", "probably", or "definitely related". For subjects with more than one event coded to the same PT, the subjects will be counted for the categories with the strongest relationship and the greatest severity. The following subject incidence tables will be presented.

- TEAEs by PT (Preferred Term) sorted by the decreasing order of subject incidence in the combined active dose group (Table 14.3.1.6)
- TEAEs by SOC (System Organ Class) and PT sorted alphabetically (Table 14.3.1.2)

- Study Drug-Related TEAEs by SOC and PT (Table 14.3.3)
- Severity of TEAEs by SOC and PT (Table 14.3.1.4)
- TESAEs by SOC and PT when applicable (Table 14.3.1.5)
- Number and percent of patients reporting common AEs (≥5% in any group) by PT (Table 14.3.1.7)
- TEAEs leading to study drug discontinuation by SOC and PT (Table 14.3.1.8)
- Treatment Emergent AESI by SOC and PT (Table 14.3.1.9)

Where warranted by the subject incidence, these same tables may be presented by treatment period (Titration, Maintenance and Conversion/Tapering).

A subject data listing will be provided for all adverse events (Listing 16.2.3.1.1). Included in the listing are the reported term, PT, SOC, TEAE flag, study day when AE starts, duration, relationship, severity, action taken, outcome, and seriousness category.

Data listings will be provided for subjects who die on study, experience SAEs, have TEAEs leading to study drug discontinuation, or AEs of special interest (Listing 16.2.3.1.2 – Listing 16.2.3.1.5).

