## 3.2.3 Conversion/Taper Phase

All subjects who complete the randomized, double blind portion of study 810P302 will have the option to participate in an OLE study (study protocol 810P304) in which all subjects will receive active SM treatment. Subjects choosing to participate will receive blinded conversion medication kits, and their total daily dose for the open label extension will be converted to 18 mg/day (Figure 1). Those subjects who do not elect to participate in this extension will be tapered off SM (Figure 2).

[figure not shown]
The 18 mg line in the 2 figures below will not be applicable to subjects re-randomized following the 810P301 interim analysis decision to drop the 18 mg dose.

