# 6.3 Analysis Populations

The population of "all enrolled subjects" consists of all those screened subjects who meet the requirements for study participation and are entered in the Baseline period of the study. The population of "all randomized subjects" consists of all those enrolled subjects who complete the Baseline Period, meet the inclusion/exclusion criteria and are randomized.

Safety Population: will include all randomized subjects who received at least 1 dose of study drug.

Intent-to-Treat (ITT) Population: will include all subjects who received at least 1 dose of study drug and have a baseline and at least 1 valid post-randomization assessment of frequency of IA behaviors based on IA diary entry.

Per-Protocol (PP) Population: will include all of the subjects in the ITT population who completed the treatment period with 80% diary completion compliance and who did not have major protocol deviations.

PK population: will include all subjects in the safety population who had at least one PK sample drawn which had a quantifiable concentration for at least one analyte of interest.

The safety, ITT, PP, and PK populations are based on randomized treatment received.

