# 6.13.1 Adverse Events

AEs will be classified into standardized medical terminology from the verbatim description (Investigator term) using the Medical Dictionary for Regulatory Activities (MedDRA). AEs will be summarized using discrete summaries at the subject and event level by system organ class and preferred term for each treatment group. Similarly, treatment-emergent AEs will be summarized by severity and relationship separately. Verbatim description and all MedDRA level terms, including the lower level terms, for all AEs will be contained in the subject data listings.

All AEs occurring after randomization and throughout the study period will be recorded. For subjects who receive SM, treatment-emergent AEs (TEAEs) will be collected starting after the first dose of SM (Visit 3) to the end of the study. These AEs include those that emerge during treatment or worsen in severity during treatment. These AEs will be tabulated, listed and analyzed.

Separate TEAE incidence tables will be presented for the three treatment groups. The incidence rates for all SADRs will also be summarized as described for all TEAEs.

In addition, these same tables will be presented by treatment period (Titration, Maintenance, and combined Titration and Maintenance). For the combined Titration and Maintenance Periods, the incidence of TEAEs will also be presented by highest severity reported and the dose of SM at first occurrence.

Listings (and tabular summaries, if warranted) of deaths, other SAEs, and other significant TEAEs, including TEAEs resulting in treatment discontinuation, will be provided.

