6.1 General Methodology

All statistical analyses will be conducted using SAS Version 9.4 or later on the Microsoft[®] Windows Operating System.

All tabulations of results will include summaries for the three treatment groups: SPN810 36mg, SPN810 18mg and placebo, however, statistical test will only include SPN810 36mg and placebo.

Continuous data will be summarized using n (number of subjects with non-missing observations), mean, median, standard deviation (SD), minimum value, and maximum value. Categorical data will be summarized using the frequency count and percentage (n, %) of subjects in each category. Number of subjects with non-missing values or number of subjects with missing values (e.g., Not Done) will be presented, where appropriate. Subjects with missing values will not contribute to the denominator of percentage calculations. Counts of zero in any category will be presented without percentage.

Treatment differences will be evaluated as SPN-810 dose minus placebo. Unless otherwise specified, all statistical hypothesis tests will be 2-sided with a significance level of α =0.05. All confidence interval will be calculated 2-sided from the unadjusted 5% significance level. P-values will be reported to 4 decimal places. P-values <0.0001 will be presented as "<0.0001". Similarly, p-values >0.9999 will be presented as ">0.9999"

The precision rules for the presentation of summary statistics will be:

- Sample size (n, N) and number of missing responses (if displayed) Integer
- Mean, median, percentiles, and confidence interval One additional decimal place than reported/collected
- Standard deviation Two additional decimal places than reported/collected
- Minimum, maximum Same number of decimal places as reported/collected
- Ratios two decimal places
- Percentages one decimal place generally, or two decimal places for <0.1%

The data summaries will be accompanied by individual subject data listings. All data available from diary, eCRF, and external transfer (labs) will be listed and will include relevant and pertinent subject information, e.g., treatment, center, age/gender/race, and study day. The listings will be sorted in the order of treatment group, unique subject ID, and assessment date/time and assessment name. The unique subject ID consists of 3-digit study number followed by digit site

number and digit subject number separated by hyphen (e.g.,

For each summary table, a supporting listing will be identified in the footnote.

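### The safety tables report the week after Visit 6 as one period by treatment group, mixing conversion with taper in every column and, on the plain reading, SPN-810 with placebo in the placebo column

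*SAP*

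**What the plan says.** **Two regimens after Visit 6.** Protocol 4.2.6 has the site dispense either Conversion or Taper medication at Visit 6, according to the family's decision about the extension. Protocol 3.2.3 says that children entering the extension "will receive blinded conversion medication kits, and their total daily dose for the open label extension will be converted to 18 mg/day", and that the others are tapered off. Protocol 3.2 has extension children enter at 18 mg/day SPN-810. Neither section excepts the placebo arm. The phase lasts one week, from Visit 6 to Visit 7.

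**One reporting period.** SAP 7.9.1 sets the adverse event periods: "AEs will be summarized using subject incidence table by treatment period (titration, maintenance, combined titration and maintenance, and tapering". Later in the same section, "these same tables may be presented by treatment period (Titration, Maintenance and Conversion/Tapering" gives the last period a second name. SAP section 4 defines the titration, maintenance and treatment periods, but not this one.

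**Three groups.** SAP 7.9: "All summaries related to safety analyses will use the safety population and will be presented by treatment groups". SAP 6.1: "All tabulations of results will include summaries for the three treatment groups: SPN810 36mg, SPN810 18mg and placebo". Protocol 6.3: "The safety, ITT, PP, and PK populations are based on randomized treatment received".

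**The event window includes the week.** Protocol 6.13.1 collects treatment-emergent events "starting after the first dose of SM (Visit 3) to the end of the study".

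**The concern.** A safety column should describe one exposure. In this week each column describes at least two.

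- **Placebo column.** It holds children on the conversion regimen together with children on the taper regimen. If conversion cards carry active tablets for placebo children, a first-exposure event, including an extrapyramidal event handled as an event of special interest, is counted under placebo.
- **36 mg column.** It holds children moving from 36 mg to 18 mg together with children moving to no drug. Withdrawal effects cannot be read from it.

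The plan has no placebo-to-SPN-810 group. The only summary by dose actually taken, in protocol 6.13.1, covers combined titration and maintenance alone. At stake is how safety findings at the end of the study are interpreted. Efficacy is not involved.

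**Working it through.** The plan gives no figure on this point, so there is none to reproduce. The check is of text, with arithmetic for scale only.

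**1. What is taken in the week.** Protocol 4.3.2 lists Taper and Conversion as separate blister cards. Protocol 4.2.6 gives one or the other. Protocol 3.2 and 3.2.3 send extension-bound children to 18 mg/day SPN-810, whatever their arm. The text does not give tablets by day; those are in Figure 1, which is not shown. A conversion kit that ends in an 18 mg/day entry dose strongly implies active tablets for placebo children within the week, but does not itemise them. For the 36 mg arm no inference is needed: one path leads to 18 mg and the other to zero.

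**2. How it is reported.** SAP 7.9.1 gives one period, SAP 6.1 gives three groups, and no section splits conversion from taper.

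**3. Which outputs draw on the week.**

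| Output | Scheduled visits or periods | Effect |
|---|---|---|
| Adverse events: titration, maintenance, combined | Separate columns | None |
| Adverse events: tapering | The week itself | Fully mixed |
| Any adverse event table without a period split | First dose to end of study | Partly mixed |
| Laboratory tests | Visits 1, 3, 6, 7 (SAP 5.4.3) | Visit 6 clean, Visit 7 mixed |
| Vital signs | Visits 1 and 7 (SAP 5.4.4) | The only scheduled post-baseline value is mixed |
| EPS scales, worse at any post-baseline visit (SAP 7.9.7) | Visits 3 to 7 (SAP 5.4.9) | Visit 7 enters the count |
| ECG | Visits 1, 4, 6 (SAP 5.4.5) | None |

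Visit 7 is also the visit for children who discontinue early (protocol 4.2.7), so its rows hold a third kind of child as well.

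**4. Scale.** Children affected = placebo arm × proportion reaching Visit 6 × extension uptake.

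- Placebo arm: about 121 of 306 (protocol 6.10).
- Reaching Visit 6: 1 − 0.20 = 0.80, from the 20% attrition in SAP 3.5.
- Uptake: not in the documents; assumed 50% to 100%.

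121 × 0.80 = 96.8, about 97 placebo completers. Then 96.8 × 0.5 = 48.4 and 96.8 × 1.0 = 96.8, so about 48 to 97 children.

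The placebo arm can also be built from the 167 and 139 children in SAP 3.5. A straight 2:1 ratio gives 167/3 + 139/3 = 102. Splitting only the former 18 mg slots 2:1 gives 167/3 + 139 × 4/9 = 117.4, about 117. The range is then 102 × 0.80 × 0.5 = 40.8 to 117 × 0.80 × 1.0 = 93.6, about 41 to 94. As a share of placebo completers, the answer is simply the assumed uptake.

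**The case against.** The strongest reply has four parts.

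- **The key fact lies in a figure not shown.** Protocol 3.2.3 speaks of the dose for the extension, and extension entry follows this week. A placebo child's conversion card might hold little or no active drug. This stands as a limit: active exposure of placebo children is inferred, not shown. It does not remove the mixture in the 36 mg column.
- **The main comparison is already protected.** Events after Visit 6 sit in their own labelled period, and combined titration and maintenance is reported separately. This stands in full.
- **A whole-study placebo count is not stated.** SAP Appendix 2 titles Tables 14.3.1.1 to 14.3.1.9 by study or treatment period. This stands in part. SAP 7.9.1 also says that by-period versions may be produced where warranted, which leaves room for unsplit tables without requiring them.
- **The table shells are a separate document, and the listings allow a later split.** Events are listed with study day, and drug accountability is listed by subject (Listing 16.2.1.8). So the information is not lost. But a reader of the tables would not see the split, and the SAP text does not call for one.

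For laboratory tests the reply is also fair: Visit 6 supplies a clean on-treatment row. Vital signs have no such row.

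**Conclusion.** The pooling is real and should be corrected. It affects one week of descriptive safety data and the summaries that draw on Visit 7. About 48 to 97 children labelled placebo would be on the conversion regimen, on the assumptions of 121 randomised to placebo, 80% reaching Visit 6 and 50% to 100% uptake. That they take SPN-810 within the week assumes that Figure 1 agrees with the plain reading of the text.

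A reader might infer three stronger things that the documents do not support:

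- **That the principal drug-versus-placebo adverse event comparison is contaminated.** It is not, because the titration, maintenance and combined columns exclude this week.
- **That active dosing of placebo children in the week is established.** It is strongly implied only.
- **That the safety difference is necessarily narrowed.** That is the direction to expect if SPN-810 raises event rates, but the documents give no event rates for the week.

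**What to change.** 1. Define the conversion/taper period in SAP section 4 and use one name for it throughout.
2. In SAP 7.9.1, report conversion and taper separately within each randomised arm. Assign children by the Visit 6 extension decision together with the dispensing and accountability record. The kit number cannot serve, because each kit holds both cards (protocol 4.3.2), and Table 1 of the protocol marks IWRS access for dispensing only at Visit 3. The dispensing record is also needed for children who stop before Visit 6 and are admitted to the extension case by case (protocol 3.2).
3. If the conversion schedule confirms active tablets, show placebo-to-SPN-810 children as active exposure. If it does not, say so in the SAP.
4. Apply the same split to the Visit 7 laboratory and vital-sign summaries (SAP 7.9.2 and 7.9.3), and identify early discontinuers separately.
5. In SAP 7.9.7, limit the any-post-baseline EPS counts to visits through Visit 6, or split Visit 7.
6. State that drug-versus-placebo statements about treatment-emergent events rest on the combined titration and maintenance period.

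The cost is SAP wording and revised shells. Three arms by two regimens gives up to 3 × 2 = 6 columns for that week, each smaller and descriptive only. No dosing, visit or data collection changes.

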7.9.2 Laboratory Test

Clinical laboratory values will be summarized by treatment group and visit using descriptive statistics for hematology, biochemistry, and urinalysis. For quantitative laboratory parameters, both actual values and change from baseline values will be summarized (Table 14.3.2.1.1, Table 14.3.2.2.1, and Table 14.3.2.3.1).

Laboratory test result will be assigned a low, normal, high (LNH) classification according to whether the value is below (L), within (N), or above (H) the reference range provided by the laboratory. Within-treatment comparisons will be based on three by three tables (shift tables), that, for a particular laboratory test, compare the LNH classification at baseline to the LNH classification at visit. By subject-listings of all laboratory values will be provided for subjects who have L or H classification in any of their laboratory tests (Table 14.3.2.1.2, Table 14.3.2.2.2, and Table 14.3.2.3.2).

Note the summary and shift tables will only use the planned/scheduled tests. However, both scheduled and repeat tests will be in the data listing.

A complete lab data listing, including hematology, biochemistry, and urinalysis will be provided for all subjects. Investigator assessment of clinical significance is based on the local laboratory reference ranges (Listing 16.2.3.2.1 – Listing 16.2.3.2.3).

7.9.3 Vital Signs, Height, Weight, and BMI

Vital signs (body temperature, heart rate, respiration rate, systolic blood pressure, and diastolic blood pressure), and their changes from baseline will be summarized by treatment group and visit (Table 14.3.3.1, Listing 16.2.3.3.1 - Listing 16.2.3.3.2). Subject body size (weight, height, and BMI) will be summarized similarly (Table 14.3.3.2, Listing 16.2.3.3.3).

7.9.4 *12-Lead ECG*

By-visit tabular summaries of the quantitative ECG parameters and the overall ECG findings (normal, abnormal not clinically significant, or abnormal clinically significant) will be presented. The QT interval will be corrected using Fridericia's method.

ECG results will be summarized by visit by treatment group using descriptive statistics (for quantitative ECG parameters) and frequency tables (for qualitative ECG parameters, including the overall ECG finding). For quantitative ECG parameters, both actual values and change from screening values will be summarized (Table 14.3.4.1 and Table 14.3.4.2).

Data listings will be presented for ECG parameters by visit. QTcF meeting the criteria of >450 but ≤480, >480 but ≤500 or >500 msec for the absolute value, or >30 msec or >60 msec increase from baseline will be identified (Listing 16.2.3.4.1 and Listing 16.2.3.4.3).

7.9.5 Columbia Suicide Severity Rating Scale (C-SSRS)

C-SSRS outcomes will be summarized using number and percent of subjects by categories for suicidal ideation only, suicidal behavior only and suicidality (ideation and behavior combined). The summary will be presented by treatment groups. (Table 14.3.5 and Listing 16.2.3.5).

7.9.6 Infrequent Behaviors Checklist

Infrequent behaviors will be listed for each subject by treatment group (Table 14.3.7 and Listing 16.2.3.7).

7.9.7 Other Special Tests

The occurrence of neurological side effects will be assessed by looking at the changes in scores from baseline to post-baseline visits for each of the Simpson-Angus scale (Table 14.3.6.1.1 - Table 14.3.6.1.2 and Listing 16.2.3.6.1), Barnes Akathisia scale (Table 14.3.6.2.1 - Table 14.3.6.2.2 and Listing 16.2.3.6.2), and AIMS (Table 14.3.6.3.1 - Table 14.3.6.3.2 and Listing 16.2.3.6.3). For each item on each of these scales, the number (and percentage) of subjects with a worse score at any post-baseline visit, compared to baseline, will be presented. A listing of these subjects will also be provided.

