# 3.2 Overall Study Design and Plan

Protocol 810P301 is a randomized, placebo-controlled, double blind, multicenter, parallel group, fixed dose study to demonstrate the efficacy, safety, and tolerability of SPN-810 in the treatment of IA in patients aged 6-12 years with ADHD in conjunction with standard ADHD treatment. The study is presented schematically in Figure 1 and Figure 2. The study is divided into three phases: Pre-Treatment, Treatment, and Conversion/Taper.

Following screening, eligible subjects will enter a flexible baseline period, at which time the IA diary will be issued to the subject's primary caregiver. At the end of the baseline period, per the original plan, eligible subjects whose primary caregiver has maintained at least 80% compliance with the IA diary will be randomized to 1:1:1 to 18 mg/day SPN-810, 36 mg/day SPN-810, or placebo. However, based on the 810P301 study Interim Analysis result decision, the 18 mg arm was dropped partway through the study. As a result, subjects planned to be randomized to the 18 mg arm will be re-allocated to the 36 mg or placebo arm in a ratio of 2:1. A dose titration schedule will be followed, with dosing in the active treatment groups initiated at 3 mg/day and increased approximately every 3 days until the target dose is reached. After completing the two-week titration period and the three-week maintenance period, subjects will enter the conversion or tapering phase prior to discontinuing SM, at which time subjects will have the option to enter an open label extension (OLE) study. A subject who discontinues during the maintenance period prior to Visit 6 may be allowed to participate in the OLE on a case-by-case basis only after consultation between the Investigator, the Medical Monitor and the Sponsor. The OLE study will be conducted under a separate protocol. Subjects who choose to participate in the OLE will enter that study at a dose of 18 mg/day SPN-810.

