# 3.2.4 End of Study / Early Termination

Subjects will return to the study site for a final visit, after completing the 1-week Taper/Conversion Period. Those subjects who elect to continue in the OLE study will have procedures performed for that study as well. Subject who discontinues from the study during the maintenance period will be offered a Taper kit and will return to the study site for a follow-up visit (EOS). Subjects who discontinue during the titration period will not receive a taper kit and will only complete the EOS procedures.

Supernus ® Pharmaceuticals, Inc.	CONFIDENTIAL	
810P302	Version 7.0	Page 43 of 225

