- 11. Collect returned SM; assess treatment compliance
- 12. Review dosing diary compliance and provide training as required
- 13. Dispense SM

## 4.2.6 Visit 6

Visit 6 will occur 21 (±3) days following Visit 5 according to the Schedule of Visits and Procedures.

- 1. Administer efficacy scales (Investigator CGI-S, caregiver and investigator CGI-I, SNAP-IV, CHQ-PF28, PSI-4-SF)
- 2. Administer Infrequent Behaviors Checklist
- 3. Administer safety scales (Simpson-Angus, Barnes Akathisia, AIMS)
- 4. Record height, weight, and BMI
- 5. Perform 12-lead ECG
- 6. Perform physical examination
- 7. Collect blood samples for hematology/chemistry
- 8. Collect urine sample for urinalysis
- 9. Administer C-SSRS
- 10. Record concomitant medication
- 11. Review IA diary compliance and provide training as required
- 12. Collect AEs
- 13. Collect returned SM; assess treatment compliance
- 14. Review dosing diary compliance and provide training as required
- 15. Determine whether subject wishes to participate in open-label extension
- 16. Dispense SM (either Conversion or Taper based upon subject's decision about participation in open-label extension)

## 4.2.7 Visit 7

Visit 7 will occur 7 (±1) days following Visit 6 according to the Schedule of Visits and Procedures. These procedures will also be performed for patients who discontinue early. Patients who discontinue early after Visit 5 will be offered a taper kit.

- 1. Administer safety scales (Simpson-Angus, Barnes Akathisia, AIMS)
- 2. Record vital signs (HR, BP, temperature, and RR), height, weight and BMI
- 3. Collect urine sample for pregnancy test (FOCBP only)
- 4. Administer C-SSRS
- 5. Record concomitant medication
- 6. Collect AEs
- 7. Collect SM and assess treatment compliance
- 8. Collect device
- 9. Complete/discontinue subject
- 10. Collect blood samples for hematology/chemistry
- 11. Collect urine sample for urinalysis

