# 6.12 Pharmacokinetic Analyses

# 6.13 Safety Analyses

Evaluation of safety will be performed for the safety population. Safety data that will be evaluated include concomitant medications, AEs, clinical laboratory results, vital signs, ECGs, and findings from the physical examinations. The occurrence of neurological side effects will be assessed by looking at any worsening in scores from Visit 3 to each subsequent visit for each of the Simpson-Angus scale, Barnes Akathisia scale, and AIMS. Suicidal ideation and suicidal behavior will be measured by C-SSRS.

All summary tables related to safety analyses will use the safety population.

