# 6.13.8 Other Special Tests

The occurrence of neurological side effects will be assessed by looking at the changes in scores from baseline to post-baseline visits for each of the Simpson-Angus scale, Barnes Akathisia scale, and AIMS. For each item on each of these scales, the number (and percentage) of subjects with a worse score at any post-baseline visit, compared to baseline, will be presented. A listing of these subjects will also be provided.

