5.4.8 Infrequent Behaviors Checklist

The infrequent behaviors checklist is a checklist of 15 behaviors that (along with the 15 IA Diary behaviors) were qualitatively linked to IA during the development of the IA diary. These behaviors include teasing, spitting, biting, weapons, ripping, breaking, vandalizing, destroying, fire setting, hitting animal, kicking self, kicking animal, severe injury self, severe injury others, severe injury animal. Caregivers will be asked which, if any, of these behaviors have been observed since the patient's last visit. This assessment will be administered at Visits 3 – 6 by the site coordinator.

5.4.9 *Extrapyramidal symptoms (EPS) scales*

The EPS symptom and neuroleptic malignant syndrome will be evaluated using the Simpson-Angus scale (Protocol Appendix 10.8), the Barnes Akathisia scale (Protocol Appendix 10.9), and the Abnormal Involuntary Movement scale (AIMS) (Protocol Appendix 10.10). The Simpson-Angus scale is a 10-item rating scale, consisting of 1 item measuring gait, 6 items measuring rigidity, and 3 items measuring glabella tap, tremor and salivation. The Barnes Akathisia scale is a rating scale for drug-induced akathisia. It includes Objective Akathisia, Subjective Awareness of Restlessness, Subjective Distress Related to Restlessness, and Global Clinical Assessment of Akathisia subscales. Additionally, total score will be calculated by summing up the Objective and two Subjective scale scores (Barnes 1989). The objective and two subjective symptoms are rated on a 4-point scale ranging from 0 to 3. The global clinical assessment is rated on a 5-point scale ranging from 0 to 4. The AIMS test is a rating scale used to measure tardive dyskinesia (Munetz 1988). It includes 12 items to rate involuntary movements of various areas of the subject's body. These assessments will be administered at Visit 3 and all subsequent visits.

6 **STATISTICAL METHODS**

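### The count of children whose EPS-scale scores worsen runs through Visit 7, after the conversion/taper week for completers, and no named summary gives a cumulative count limited to titration plus maintenance

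*SAP*

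**What the plan says.** SAP 7.9.7 (Other Special Tests) describes the EPS scales through changes from baseline and then, item by item, says that "the number (and percentage) of subjects with a worse score at any post-baseline visit, compared to baseline, will be presented", with a listing of those children. Protocol 6.13.8 uses the same rule ("subjects with a worse score at any post-baseline visit, compared to baseline, will be presented"). Protocol 6.13 describes the assessment as "looking at any worsening in scores from Visit 3 to each subsequent visit". None of the three sets a last visit or ties the count to the last dose of randomised treatment.

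On the schedule, SAP 5.4.9 says of the three scales: "These assessments will be administered at Visit 3 and all subsequent visits". Protocol 4.2.7 lists them first among the Visit 7 procedures ("Administer safety scales (Simpson-Angus, Barnes Akathisia, AIMS").

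On what precedes Visit 7, protocol 3.2.4 says: "Subjects will return to the study site for a final visit, after completing the 1-week Taper/Conversion Period". Protocol 3.2.3 gives two tracks. Of those entering the extension it says: "Subjects choosing to participate will receive blinded conversion medication kits, and their total daily dose for the open label extension will be converted". The figure it names is 18 mg/day. The others are tapered off. SAP 3.3.2 lists a five-week treatment phase (titration and maintenance) and a separate one-week conversion/tapering phase. The definitions table in SAP section 4 likewise makes the Treatment Period titration plus maintenance, with maintenance ending at Visit 6, although it words those limits for the IA diary.

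**The concern.** Safety is part of the primary objective, and protocol 3.1 says these scales were chosen specifically to monitor EPS. The any-visit figure is the only cumulative, subject-level summary of scale worsening that the SAP text specifies. It is tabulated by arm but combines two periods: five weeks on the assigned regimen, and one week on a conversion or taper kit that depends on whether the child enters the extension. A reader of the table could take it as the rate of worsening on 36 mg or on placebo during randomised treatment. A child whose score first worsens at Visit 7 would be counted in the same way as one who worsened during maintenance. The SAP avoids this for adverse events: section 7.9.1 splits them into titration, maintenance, the two combined, and tapering.

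**Working it through.** The plan states no figure to reproduce. The check is of schedule and text, with one short calculation.

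**1. Which visits count.** SAP section 4 defines baseline as the last non-missing value before first dose, which is Visit 3 for these scales. Scheduled post-baseline assessments are therefore Visits 4, 5, 6 and 7 (Days 8, 15, 36 and 43 in the schedule table). Visit 7 is 1 of 4.

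**2. Where Visit 7 falls.** Protocol 4.2.7 puts it 7 (±1) days after Visit 6. At Visit 6 the scales are done and conversion or taper medication is dispensed (protocol 4.2.6). For a completer, Visit 6 therefore closes maintenance and Visit 7 follows the kit week.

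**3. Who is an exception.** Protocol 4.2.7 applies the Visit 7 procedures to early discontinuers too. Under protocol 3.2.4, children who stop during titration get no taper kit, while those who stop during maintenance are offered one. The final assessment of a child who took no taper medication does not follow a taper. A child who stops before Visit 4 may have no other post-baseline EPS assessment. A cut by visit number alone would lose that child.

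**4. Whether the named tables supply the missing count.** SAP Appendix 2 lists six EPS-scale tables. Tables 14.3.6.1.1, 14.3.6.2.1 and 14.3.6.3.1 give item scores and change by visit. Tables 14.3.6.1.2, 14.3.6.2.2 and 14.3.6.3.2 give shift from baseline by visit. None is titled as cumulative or by period.

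By-visit counts only bound a cumulative count, because one child may be worse at several visits:

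- lower bound = the largest single-visit count;
- upper bound = the sum of the single-visit counts.

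As an illustration, assume 5% of children are worse at each visit (this rate is not in the documents):

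- Visits 4 to 6, bounds: 5% to 3 × 5% = 15%;
- Visits 4 to 6, if visits were independent: 1 − 0.95³ = 14.3%;
- Visits 4 to 7, if visits were independent: 1 − 0.95⁴ = 18.5%.

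The same by-visit tables are compatible with any through-Visit-6 figure from 5% to 15%. They do not fix it.

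**5. Whether the adverse-event tables replace it.** Table 14.3.1.9 gives adverse events of special interest by treatment period. Protocol 5.4 leaves it to the investigator whether a positive scale finding is recorded as an adverse event, and protocol 5.4.3 says such a finding need not be an EPS event. That table counts something else.

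**The case against.** The strongest reply is that this is a choice and not an error. The SAP and protocol agree with each other. Counting to the end of blinded follow-up is a defensible, inclusive safety rule: protocol 6.13.1 collects treatment-emergent events to the end of the study, protocol 4.3.8 keeps the blind through conversion/taper, and protocol 4.3.6 even refers to a six-week treatment phase. The by-visit shift tables already show Visit 7 on its own, the promised listing would let anyone derive the cumulative count, and row definitions would normally sit in the shells, which are a separate document (SAP Appendix 3).

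Most of this stands. It is the reason to keep the all-visits count and to treat the point as minor. It also rules out the reading that the plan hides Visit 7 or gives no subject-level information before it. What it leaves open is narrower: a listing is not a summary, and the by-visit tables cannot produce the cumulative figure for titration plus maintenance.

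A reader might also infer that the between-arm comparison is contaminated, with 36 mg children off their maintenance dose and placebo children on active drug by Visit 7. The documents do not establish this. Protocol 3.2 says: "Subjects who choose to participate in the OLE will enter that study at a dose of 18 mg/day SPN-810". That is the dose on entering the extension; doses day by day in the conversion or taper week are in figures not shown in the copy reviewed.

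**Conclusion.** The point holds as a minor reporting gap. The any-visit count includes Visit 7, which for completers lies after the conversion/taper week, and no summary named in the SAP text or Appendix 2 gives a cumulative subject-level count of scale worsening limited to titration plus maintenance.

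The only size the documents support is that Visit 7 is one of four scheduled post-baseline assessments. They give no rate of first worsening at Visit 7, so a number of extra cases cannot be stated, and either arm could gain them. It should not be read as evidence of bias for or against 36 mg. No efficacy result, test or error rate is involved.

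The conclusion rests on the SAP text and Appendix 2. If the shells already define a period-limited row, the point is met by citing them.

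**What to change.** In SAP 7.9.7, keep the all-visits count and add two rows per item:

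- **(a)** children worse than baseline at any assessment made before the first conversion or taper dose, including the end-of-study assessment of early discontinuers who took no taper medication;
- **(b)** children worse than baseline at an assessment made after conversion or taper dosing began.

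Define the split by the date of that first dose and not by visit number, and name its source; protocol 3.1 says administration is recorded in an electronic dosing diary. State each row's denominator. Footnote that a child can appear in both rows, so the all-visits count equals (a) plus (b) minus those in both. This follows the period split already used for adverse events in SAP 7.9.1.

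The cost is SAP wording and programming, with no new visits or procedures. The downside is longer tables.
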